1.3 SCHEDULE OF ACTIVITIES

Study Phase	Screening & Baseline 5																					I	nterv	entio	n												
Day Number 1							6	10	11	12	13	14	15	16	17	18	19	20	21	22	23	24	25	26	27	28	29	30	31	32	33	34	35	36			
Visit Number	٧1	v2 ⁶							٧3							٧4							٧5							9^							٧٧
Informed consent	Х																																				
Eligibility Confirmation	Х	х																																			
Vision Testing	Х																																				
Psychological assessment		Х																																			
Accelerometry		Χ	Χ	Χ	Х	Х	Х	Х	Х	Χ	Χ	Х	Х	Χ	Х	Х	Х	Х	Χ	Χ	Χ	Х	Х	Χ	Χ	Χ	Χ	Χ	Х	Х	Χ	Χ	Χ	Χ	Χ	Х	Χ
PSQI									Х														Х														Χ
Daily log ²		Х	Х	Х	Х	Х	Х	Х	Х	Χ	Х	Х	Х	Х	Х	Х	Х	Х	Х	Χ	Χ	Х	Х	Х	Χ	Χ	Χ	Χ	Х	Х	Χ	Χ	Χ	Х	Х	Х	Χ
Urine screen ³	Х	х							Х														Х														Χ
Breathalyzer	Х	Х							Х							Х							Х							Х							Χ
Clinician-administered assessments									х														Х														Х
Self-report questionnaires									Х							X ⁷							Х							X ⁷							Х
fMRI ⁴									Х																												Χ
Randomization									Х																												
Treatment expectation									Х																												
Light therapy										Χ	Х	Х	Х	Х	Х	Х	Х	Х	Х	Х	Х	Х	Х	Х	Х	Χ	Х	Χ	Х	Х	Χ	Χ	Х	Х	Х	Х	Х
Treatment fidelity – daily contact										Х	Х	х	х	Х	х	Х	х	х	Х	Х	Х	Х	Х	Х	Х	Х	Х	Х	х	х	Х	Х	Х	Х	Х	Х	Х
Treatment fidelity – data download & feedback																х							х							х							Х
AE Assessment (SAFTEE/CSSRS)	х	х							Х							Х							Х							Х							Х
Treatment satisfaction																																					Χ

^{1 –} Exact day number can vary by up to one week; 2 – Daily log will capture information about sleep time, treatment time, medication use, etc.; 3 – Urine drug screen administered via dipstick by study team at baseline and urine pregnancy screen to ensure drug free participants; 4 – fMRI must occur within 7 days of clinician-administered assessments; 5 – Final screening and eligibility confirmation occur on day 0/v1 and the start of the weeklong baseline period begins at v2; 6 – Visit 2 activities may be split across 2 days separated by no more than 1 month; 7 – Only the PCL-5 and DASS will be administered at these visits

2 Introduction

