5 STUDY DESIGN

5.1 OVERALL DESIGN

- Single-blinded randomized controlled mechanistic trial
- Parallel groups
- 3 study arms based on light treatment duration: 15-minutes, 30-minutes or 60-minutes/day
- 4-weeks of morning bright light treatment delivered via Re-Timer device

This is a 5-week study (1-week of baseline and 4-weeks of intervention) that includes a screening visit plus 6 additional study visits to evaluate outcomes and monitor progress. Potential participants are prescreened for major exclusion criteria using a combination of online and telephone surveys. On Day 0 (Visit 1) individuals are consented and eligibility confirmed using several self-report questionnaires. Final eligibility is confirmed after the clinician interviews on visit 2 do not reveal any exclusionary psychiatric conditions (see below).

Participants return to the lab for study visit 2 for a battery of psychological assessments to characterize the sample, and to begin the week-long baseline period (see Section 1.3 - Schedule of Activities). At this visit, participants are provided with their study materials (Actiwatch Spectrum, daily log, instructions to sleep according to a normal schedule, etc.). To minimize burden participant burden and to accommodate calendar challenges (e.g. time change), the activities for this visit may be split across 2 days such that the psychological assessments are done on one day and the distribution and training of study materials occur on a second day within 1 months' time.

On Day 8 (Visit 3) participants return to the lab for randomization and baseline outcome assessments. Morning light treatment begins on the morning of Day 9. Thereafter, participants come to the research lab weekly to assess adherence to the study procedures and intervention, and monitor for side effects. Outcome assessments occur on Day 8, Day 22 (week 2 of intervention) and Day 36 (week 4 of intervention). The exact day number of study visits and activities can vary by up to a week; and we will try to schedule study visits for the same time of day. While the plan is to schedule the fMRI for the same day as the psychological assessments, we do allow for a 7-day window in cases where same-day scheduling is not possible.

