9.7 FMRI

Amygdala reactivity will be measured using fMRI and change in BOLD signal measures across the study period. Images will be acquired using an Echo-Planar Imaging sequence (TR=800 ms, FOV=23, slice=2.4mm, 96x96 matrix) to measure brain function at rest and during the EFAT task, optimized to reduce susceptibility artifact. fMRIs (initially at visits 3, 5 and 7 but later changed to only visits 3 and 7) will be scheduled at the North Campus facility and must occur within 7 days of the clinician-administered and self-reported assessments of trauma stress and mood (see Section 9.3)

9.7.1 fMRI Practice

As part of the screening process, individuals will be able to lie in the mock scanner located at the Rachel Upjohn Building. This scanner is built to size, and includes simulating scanner noise from speakers so people can hear the noises associated with scanning.

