11 STATISTICAL CONSIDERATIONS

11.1 GENERAL APPROACH

The objective of this study is to establish a signification dose response relationship between the duration of morning light treatment and reduction in amygdala reactivity from baseline to treatment week 2 (study week 3) and/or treatment week 4 (study week 5).

Statistical analyses will include intent-to-treat and completer analysis. Data will be analyzed using responses at all three times (baseline, 2 [when data available] and 4 weeks) as dependent variables using a mixed-effects longitudinal model [106, 107] with participants as random intercepts to account for between participant variability and time as a predictor.

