11.2 ANALYSIS OF PRIMARY OUTCOME

We will first graphically explore the relationship between responses and dose by time and specify how dose and time will be parameterized. For example, if a linear dose-dependent relationship is shown at each follow-up time (e.g., incremental drop in amygdala reactivity with increasing duration of daily light pulse), we will assess it by including dose (in minutes) and will include the interactions of time by dose to assess how/if the relationship changes over time (e.g., no difference across groups at baseline and dose-dependent relationship at weeks 2 and 4). A test of overall dose response relationship between duration of daily light pulse and reduction from baseline in amygdala reactivity will be established based on the significance of the interaction term. Time can also be included as categorical indicators to see, for example, if 4 weeks, relative to 2 weeks achieve even greater (or no greater) response.

If a nonlinear dose-dependent relationship is shown in graphs, it will be explored using indicators of dose groups. If the relationships at 2 weeks differ from those at 4 weeks, we will analyze them using separate models.

Statistical analysis will be performed using SAS 9.3. Regarding missing data, if "non-ignorable" patterns are detected, then "pattern mixture", "selection models", or other appropriate strategies will be used to examine the impact of the missing data pattern on the key outcomes [108, 109]. All analyses will include tests for sex differences, in order to examine sex as a biological variable.

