11.3.2 Traumatic stress symptoms

We will also examine the clinician-administered (PSSI-5, HAM-D, HAM-A) and self-report measures (DASS, PCL-5) of traumatic stress symptoms with a mixed-effects longitudinal regression model as described above.

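### A random-intercept-only model, reused for outcomes with three or more visits, can understate the standard error of the baseline-to-week-4 dose contrast

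*Combined protocol and SAP*

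**What the plan says.** Section 11.1 sets out a longitudinal mixed model for baseline, week 2 (where collected) and week 4, "with participants as random intercepts to account for between participant variability and time as a predictor". Section 11.2 judges the overall dose response "based on the significance of the interaction term", with dose in minutes if the relationship looks linear. The coding of time is left open: "Time can also be included as categorical indicators to see" whether week 4 adds to week 2.

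Section 11.3.2 carries the model over to three clinician-rated scales (PSSI-5, HAM-D, HAM-A) and two self-report scales (DASS, PCL-5). It gives the method only by reference back: "with a mixed-effects longitudinal regression model as described above".

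The number of visits differs by outcome:
- PSSI-5, HAM-D and HAM-A: three. Section 5.1 says "Outcome assessments occur on Day 8, Day 22 (week 2 of intervention) and Day 36 (week 4 of intervention"), which are Visits 3, 5 and 7.
- PCL-5 and DASS: five, Visits 3 to 7. The schedule in section 1.3 marks self-report at Visits 4 and 6, with the footnote "Only the PCL-5 and DASS will be administered at these visits".
- Amygdala scans: section 9.7 says "initially at visits 3, 5 and 7 but later changed to only visits 3 and 7". Some early participants may therefore have three scans; how many is not stated.

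No random slope, residual covariance structure, robust standard error or small-sample degrees-of-freedom method appears anywhere.

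**The concern.** A random-intercept model with independent residuals assumes that scores four weeks apart are as strongly correlated as scores one week apart, and that participants in the same dose arm share one time trend. It pools all within-person variation into one residual variance and uses that for the standard error of change. If neighbouring visits are more alike than distant ones, or if participants improve at different rates, baseline-to-week-4 change is more variable than the pooled figure implies.

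Both departures are plausible here. Section 3.1.2 says distress symptoms in this population tend to fluctuate, and section 11.3.3 plans to examine whether diagnosis moderates response. At stake are intervals that are too narrow and too many false dose-response signals in the symptom scales. The scan analysis is exposed to a smaller degree, through any week-2 scans kept in the model.

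**Working it through.** The plan gives no power, alpha, variance or within-person correlation for this analysis, so there is no figure to reproduce. Inputs from the documents are 66 participants (section 6), doses of 15, 30 and 60 minutes (section 7.2) and the visit schedules above. Assumed here: 22 per arm, complete data, a two-sided 5% test, and the covariances listed.

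**Formulas.** Let S be the true within-person covariance at T visits, P the centring matrix and c centred time. In balanced data the random-intercept fit estimates s² = tr(PS)/(T−1). With unit variance at each visit, this is 1 minus the mean pairwise correlation. The ratio r of true to assumed variance is:
- week-4 minus baseline contrast: r = (S₁₁ + S_TT − 2S₁T)/(2s²)
- linear dose-by-time term: r = c′Sc/(c′c · s²)

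Type I error = 2[1 − Φ(1.96/√r)]. With T = 2, s² is exactly half the variance of the change, so r = 1 and the test runs at 5% whatever the covariance.

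**Worked example: AR(1), weekly correlation 0.8, no measurement noise.**
- Three visits. Correlations are 0.64, 0.64 and 0.4096, so s² = 1 − 0.5632 = 0.4368. r = (1 − 0.4096)/0.4368 = 1.352, giving 9.2%. Linear and week-4 contrasts coincide with three equally spaced visits.
- Five visits. The mean correlation is 6.5536/10 = 0.6554, so s² = 0.3446. Week-4 contrast: r = 0.5904/0.3446 = 1.713, giving 13.4%. Linear term: c′Sc = 7.747 and c′c = 10, so r = 0.7747/0.3446 = 2.248, giving 19.1%.

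**Same scenario with visit-specific noise** (variance shares: intercept 0.4, AR(1) 0.3, noise 0.3).
- Three visits: s² = 0.3 × 0.4368 + 0.3 = 0.4310. r = (0.3 × 0.5904 + 0.3)/0.4310 = 1.107, giving 6.2%.

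**Range of assumptions (type I error, %).**

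| Assumed covariance | 3 visits | 5 visits, week-4 contrast | 5 visits, linear |
|---|---|---|---|
| Equal correlation | 5.0 | 5.0 | 5.0 |
| AR(1) 0.5 | 6.8 | 9.2 | 13.6 |
| AR(1) 0.7 | 8.3 | 11.9 | 17.3 |
| AR(1) 0.9 | 10.1 | 15.0 | 20.8 |
| Slope SD over 4 weeks = 0.5 × residual SD | 5.7 | 6.0 | 6.3 |
| Slope SD = 1 × residual SD | 7.4 | 8.5 | 9.8 |
| Slope SD = 2 × residual SD | 11.0 | 14.9 | 18.2 |
| Intercept 0.5, AR(1) at 0.8 0.3, noise 0.2 | 6.6 | 7.9 | 10.1 |
| Intercept 0.4, AR(1) at 0.8 0.3, noise 0.3 | 6.2 | 7.2 | 8.8 |
| Intercept 0.3, AR(1) at 0.8 0.2, noise 0.5 | 5.6 | 6.0 | 6.8 |

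Adding a random intercept to AR(1) without noise changes nothing, because the intercept cancels from within-person change.

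**Simulation checks.** With 20,000 replicates the linear test ran at 8.4% (three visits) and 17.9% (five) under AR(1) 0.7, and at 10.2% and 21.0% under AR(1) 0.9. A joint test of all categorical time-by-dose terms stayed at about 5–8%. A test on each participant's own fitted slope stayed at 4.5–5.3% throughout.

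**Scan model with partial week-2 data** (REML random intercept, categorical time, week-4 contrast, 3,000 replicates, AR(1) without noise). With week-2 scans on 25%, 50% and 100% of participants, the error was 7.0%, 8.4% and 10.3% at weekly correlation 0.85, and 6.0%, 6.8% and 8.5% at 0.7. With two scans only it was 5.0%. Measurement noise would lower the inflated figures.

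**The case against.** The strongest reply is that nothing in the documents shows that the equal-correlation assumption fails. That stands. A reader might infer that the planned standard errors are wrong and that all symptom intervals are too narrow; without any stated covariance, only that they can be is supportable. Even a plausible fall in correlation does not fix the size. A week-4 correlation of about 0.52 or 0.62 with realistic noise gives 6–10%, not 10–20%.

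A reader might also take 20% as the error rate of the plan. It applies only to PCL-5 and DASS, only with linear time, and only if all five scores enter. Section 11.1 describes three times, and nothing says the Visit 4 and 6 scores join this model, so the five-visit case is an inference.

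Nor do the documents support reading this as a threat to the primary result or to the phase transition. Scanning is now at two visits, where the test is exact. Section 11.2 moves to separate week-2 and week-4 models if those relationships differ, which is partial protection. The go/no-go rule in section 11.1.2 is an effect size of d ≥ 0.5, not this p-value. The symptom analyses sit under exploratory analyses.

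What remains is that the stated model has no safeguard against a common departure. Separate models and categorical time are optional or conditional, and categorical time alone does not protect the week-4 contrast.

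**Conclusion.** The point holds conditionally. As written, the model can understate the standard error of the baseline-to-week-4 dose contrast for any outcome with more than two visits. For an assumed two-sided 5% test with 66 participants, three visits give about 5–10% (11% in the most extreme slope case tried). Five PCL-5 or DASS scores, if all are used, give about 6–15% for the week-4 contrast and up to about 20% for a linear dose-by-time term. The upper ends need strong serial correlation with little measurement noise, or slope variation well above residual variation. Equal correlation gives 5%.

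The scan analysis runs at about 5–10%, depending on how many week-2 scans are retained. The weight is moderate: the symptom outcomes are exploratory, but section 4 makes a significant dose response the objective of this phase, and the correction is cheap.

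**What to change.** In section 11.3.2, state which visits enter each symptom model. Specify categorical visit, dose and their interaction, with an unstructured within-participant covariance, REML and Kenward-Roger degrees of freedom, and take the week-4 dose contrast from that model. If it does not converge, use random intercept plus slope, or robust standard errors with a small-sample correction.

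In section 11.1, use the same unstructured model for the scans. If the week-2 entries cannot be estimated, base the week-4 dose test on baseline and week-4 scans only, either as a two-time model or as the week-4 value adjusted for baseline. A random slope is not a usable fallback here. With two scans per participant it needs four covariance parameters (intercept variance, slope variance, their covariance and the residual) from three observable moments, so it would rest entirely on the unknown number with three scans.

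The cost is a wording change and a small change to the planned SAS code, with no new data. Intervals become slightly wider if correlation does fall with time. Covariance parameters rise from 2 to 6 with three visits (3 × 4/2) or 15 with five (5 × 6/2).

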11.1.1 Hypothesis

There will be a significant dose response relationship between light duration and reduction in amygdala reactivity.

11.1.2 Go/No-go Criteria

A meaningful reduction in amygdala reactivity (Cohen's d≥0.5) must be observed with one of the three daily light durations at treatment week 2 and/or treatment week 4.

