1 PROTOCOL SUMMARY

1.1 SYNOPSIS

Title:	Morning Light Treatment for Traumatic Stress: The Role of Amygdala Reactivity
Study Description:	Participants will be enrolled in a 3-arm randomized controlled trial of a 4-week self-administered wearable morning light treatment to evaluate the dose-response association between amount of light therapy (15, 30 or 60 minutes per day) and the degree of brain reactivity in the amygdala in response to an emotional faces fMRI task.
Primary Objective	Average blood-oxygen-level-dependent (BOLD) percent signal change in the bilateral amygdala from baseline to week 2 and/or baseline to week 4 of treatment.
Study Population:	Individuals with traumatic stress and significant distressing symptoms
Phase:	n/a
Description of Sites/Facilities Enrolling Participants:	University of Michigan Sleep and Circadian Research Lab & North Campus fMRI suite
Description of Study Intervention:	Daily self-administered morning light therapy delivered using a commercially available device, the Re-Timer.
Study Duration:	3 years
Participant Duration:	5 weeks

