4 OBJECTIVES & ENDPOINTS

This study is a part of a larger proposal under the NIH R61/R33 mechanism which requires specific Go-No Go Criteria to transition between the two phases of the proposal. This protocol is specific to the R61 Phase. The specific aim and **objective for this phase** (i.e. study) is to **establish a significant dose response relationship between duration of morning light pulse and reduction in amygdala reactivity** from baseline to week 2 and/or week 4.

The **endpoint is whole-brain oxygen-level-dependent (BOLD) fMRI signal** using a priori regions of interest **specific to the bilateral amygdala**.

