6.5 Participant Incentives

Participants are eligible for up to \$1210.00 in incentive payments. The payment plan was designed to partially compensate individuals for the burden of the study visits and associated travel costs, as well as promote study completion by including a bonus for finishing the protocol. Participants will be paid as the study progresses for those parts of the study completed.

- Visit 1 \$20 for screening visit eligibility confirmation and consent
- Visit 2 Receive study materials, no incentive
- Visit 3 \$225
 - \$75 for completing the baseline week of actigraphy and activity/sleep logs
 - \$150 for completing the clinical assessments and fMRI
- Visit 4 \$75 for completing previous week of actigraphy and activity/sleep logs
- Visit 5 \$175
 - \$75 for completing previous week of actigraphy and activity/sleep logs
 - \$100 for completing clinical assessments
- Visit 6 \$75 for completing previous week of actigraphy and activity/sleep logs
- Visit 7 \$400
 - \$75 for completing previous week of actigraphy and activity/sleep logs
 - \$150 for completing clinical assessments and fMRI
 - \$175 bonus for completing the study
- Travel stipend \$80 \$240 for Visit 1-7 (e.g. up to 8 visits to the research clinic including coming to the clinic twice for activities associated with Visit 2)
 - The travel stipend will be \$10 \$30 per study visit to account for the varying distance which different participants must travel to the lab. The travel stipend will always be at least \$10, increasing by approximately \$1 per mile traveled, up to a maximum of \$30 for 30 miles or more. Mileage will be rounded up to the nearest whole number to determine the dollar amount given, e.g., 10.4 miles would amount to a travel allowance of \$11.
 - Participants will be asked to verify from which location they will be traveling to lab visits during their phone screen and reconfirm this at Lab Visit 1, which will determine their stipend for Visits 1-7.

o If the fMRI occurs on a different day from the research clinic visit, the travel stipend is only provided for the visit to the clinic (e.g. Rachel Upjohn Building).

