9.9 OTHER RESEARCH PROCEDURES

9.9.1 Urine drug/pregnancy screen

All female participants of childbearing age take a urine pregnancy test at visit 1, visit 5, and every visit with an fMRI; additionally, we will also do a dip stick drug screen to assess for illicit drug use on all participants during lab Visits 1, 2, 5, and at every visit with an fMRI.

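### The Go criterion and the objective still accept a week-2 result although the week-2 scan was dropped, so a partial week-2 sample can meet the criterion when the scheduled week-4 scan does not

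*Combined protocol and SAP*

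**What the plan says.** Section 11.1.2 sets the Go/No-Go criterion: an observed reduction of Cohen's d of at least 0.5, which "must be observed with one of the three daily light durations at treatment week 2 and/or treatment week 4". Section 4 explains that such criteria are required to move from the R61 to the R33 phase.

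The objective uses the same time points. Section 1.1 measures change "from baseline to week 2 and/or baseline to week 4 of treatment", section 4 seeks a dose-response in the reduction "from baseline to week 2 and/or week 4", and section 11.1 repeats this.

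The scan schedule differs. Section 9.7 says the fMRI sessions were "initially at visits 3, 5 and 7 but later changed to only visits 3 and 7". Three other places agree:

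- The fMRI row of the schedule in 1.3 marks Visits 3 and 7 only.
- In 6.5 the Visit 5 payment includes "100 for completing clinical assessments" with no scan, while the payments for Visits 3 and 7 cover both.
- Section 9.9.1 requires pregnancy tests "at visit 1, visit 5, and every visit with an fMRI", which lists Visit 5 apart from the fMRI visits.

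Section 5.1 identifies Day 22 (Visit 5) as week 2. The model in 11.1 was adapted to the change, with responses at "baseline, 2 [when data available] and 4 weeks". Section 11.2 adds: "If the relationships at 2 weeks differ from those at 4 weeks, we will analyze them using separate models".

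**The concern.** The analysis model was adjusted when the week-2 scan was dropped, but the decision rule and the objective were not. Week 4 is now the only post-baseline scan scheduled for every participant, yet the rule still gives equal standing to a visit at which an unstated part of the sample was scanned.

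The criterion is a bare point-estimate threshold with no test, confidence interval or minimum n. Such a threshold is easier to reach by chance as the sample gets smaller. Dropping the scan part-way therefore loosened the criterion without the text saying so. The question of which visit counts is also left open until results are known, and 7.4.2 leaves the PI unblinded to arm.

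**Working it through.** The plan gives no false-Go rate, power or SD, so there is no stated figure to reproduce. What can be computed is how the written rule behaves.

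**Inputs from the documents.** 66 enrolled (section 6); three arms (5.1, 7.4.1); threshold d ≥ 0.5, any one arm, week 2 and/or week 4 (11.1.2).

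**Assumptions.** Equal allocation, 66/3 = 22 per arm; no dropout; no true change in any arm; 5, 12 or 22 per arm scanned at week 2, nested in the 22. The true week-2 number is not given.

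**Case 1: complete cases, d = mean change / SD of change.** An observed d ≥ 0.5 is the same event as t ≥ 0.5√n on n−1 degrees of freedom. With p the chance in one arm, the chance in any of three is 1 − (1 − p)³.

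| n per arm | 0.5√n | p, one arm | any of three |
|---|---|---|---|
| 22 | 2.345 | 0.0145 | 0.043 |
| 12 | 1.732 | 0.0556 | 0.158 |
| 5 | 1.118 | 0.163 | 0.414 |

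Counting both visits needs simulation (200,000 runs), with the two change scores correlated at 0.3 to 0.7:

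| Week-2 n per arm | Met at week 4 | Met at either visit | Met at week 2 only |
|---|---|---|---|
| 5 | 4.3% | 43–44% | about 39% |
| 12 | 4.3% | 18–19% | 14–15% |
| 22 | 4.3% | 7–8% | 3–4% |

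The last column is the chance that some arm passes at week 2 while no arm passes at week 4.

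Two effects are mixed here. At correlation 0.5, allowing two visits with everyone scanned raises 4.3% to 7.9%. That part was already in the rule before the scan was dropped. Shrinking the week-2 sample raises it further, to 18.8% with 12 per arm and 43.3% with 5.

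**Case 2: mixed-model arm-by-time means, d = change / baseline SD.** Scores at the three times are assumed equally correlated at r. The week-2 mean is then the mean of those scanned plus r/(1+r) × [(baseline mean of all 22 − baseline mean of those scanned) + (the same difference at week 4)]. Chance of meeting the criterion (100,000 runs, r treated as known):

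| SD | r | Week 4 alone | Either visit: 5 / 12 / 22 per arm |
|---|---|---|---|
| per arm | 0.3 | 8.6% | 39.7 / 22.6 / 15.1% |
| per arm | 0.5 | 4.2% | 30.9 / 13.7 / 7.8% |
| per arm | 0.7 | 1.0% | 17.1 / 4.7 / 1.8% |
| pooled | 0.3 | 7.3% | 38.2 / 20.6 / 13.1% |
| pooled | 0.5 | 3.3% | 29.2 / 11.7 / 6.0% |
| pooled | 0.7 | 0.5% | 15.4 / 3.3 / 1.0% |

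Estimating r by REML (20,000 runs, SD per arm) gave either-visit values within half a percentage point of these.

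Within each definition, counting week 2 raises the chance by about 1.7 to 2 times if all 22 per arm were scanned, and by more the fewer were scanned.

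**The case against.** **The rule can still be executed.** Sections 9.7 and 11.1 disclose the change openly, the early week-2 scans are legitimate study data, and the text does not show whether the and/or wording was kept on purpose. This is true, but a rule that can be executed is not thereby well defined: nothing says which visit governs when they disagree.

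**The size is not established.** The largest figures need 5 per arm and one particular d. With r = 0.7, pooled SD and 12 per arm, the either-visit chance is 3.3%, below the 4.3% for week 4 alone under the other definition. Section 11.3.1 mentions an effect-size comparison in addition to the mixed model, so the plan does not settle the source of d. This stands: no single figure is the rule's error rate. The like-for-like comparison under that same definition is still 0.5% against 3.3%.

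**The criterion is necessary, not sufficient.** The dose-response hypothesis is tested by the interaction term (11.2), and the separate week-2 model there is conditional. This also stands, and it limits the consequence. A necessary condition still has to screen something.

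**Week 4 alone misses real effects.** Suppose a true d of 0.5 at both visits in one arm and none in the others (22 per arm, correlation 0.5, SD of change). Week 4 alone then meets the criterion about 52% of the time, against about 82%, 74% and 70% at either visit with 5, 12 and 22 per arm scanned at week 2. The loss is real. But the apparent advantage grows as the week-2 sample shrinks, so much of it is noise rather than sensitivity.

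**Another remedy exists.** Week 2 could stay, with a minimum n per arm and a rule for discordant visits. Section 2.1.2 does give a rationale for effects by 2 weeks. This would also close the gap, but the minimum would be chosen after the week-2 sample is already fixed.

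**Conclusion.** The concern holds, and the text should be corrected before amygdala change is examined by arm. The current schedule provides one post-baseline scan, at week 4, while 1.1, 4, 11.1 and 11.1.2 still accept week 2. Followed exactly, the plan lets one arm's week-2 estimate from an unstated subset satisfy the R61-to-R33 criterion when the scan scheduled for everyone fails it in all three arms.

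That conclusion rests on the text, not on any percentage. It assumes only that some week-2 scans exist, which the wording in 11.1 implies. The size depends on the week-2 n, the definition of d and its estimator, none of which the plan states. With no true change, the chance of passing at week 2 only ranged from about 0.5% (22 per arm, mixed model, r = 0.7, pooled SD) to about 39% (5 per arm, complete cases).

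**What to change.** - In 1.1, 4, 11.1 and 11.1.2, make change from baseline to week 4 the sole basis for the primary objective and the Go criterion.
- Keep the available week-2 scans in the mixed model and report them as supportive, with n per arm.
- In 11.2, label any separate week-2 model as supportive.
- While amending 11.1.2, name the SD and the estimator for d and require its 95% CI. This is a side point that applies equally at week 4.

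The cost is a wording amendment with no new data. The second chance to meet the criterion at week 2 is lost, as quantified above. A funder milestone would be reworded after some scans were collected and with the PI unblinded to arm. The change is in the stricter direction, but the funder must be told, and the amendment should be dated before amygdala change is examined by arm.
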